9.2.2 Serious adverse events (SAEs)

A serious adverse event is any adverse event that led to any of the following:

- Death,
- Serious deterioration in the health of the subject, that resulted in any of the following:
 - o Life-threatening illness or injury,
 - o Permanent impairment of a body structure or a body function,
 - o Hospitalisation or prolongation of patient hospitalisation,
 - o Medical or surgical intervention to prevent life-threatening illness or injury or permanent impairment to a body structure or a body function,
 - o Chronic disease,
- Foetal distress, foetal death or a congenital physical or mental impairment or birth defect.

An elective hospital admission will not be considered as a serious adverse event.

The investigator will report all SAEs to the sponsor without undue delay after obtaining knowledge of the events. The sponsor will report the SAEs through the web portal *ToetsingOnline* to the accredited METC that approved the protocol, within 7 days of first knowledge for SAEs that result in death or are life threatening followed by a period of maximum of 8 days to complete the initial preliminary report. All other SAEs will be reported within a period of maximum 15 days after the sponsor has first knowledge of the serious adverse events.

9.2.3 Suspected unexpected serious adverse reactions (SUSARs)

Not applicable.

9.3 Annual safety report

Not applicable.

9.4 Follow-up of adverse events

All AEs will be followed until they have abated, or until a stable situation has been reached. Depending on the event, follow up may require additional tests or medical procedures as indicated, and/or referral to the general physician or a medical specialist. SAEs need to be reported till end of study within the Netherlands, as defined in the protocol.

9.5 Data Safety Monitoring Board (DSMB) / Safety Committee

Not applicable.

10. STATISTICAL ANALYSIS

Demographic data and patient-reported data will be registered and saved in Castor by the coordinating investigator. Database cleaning will be carried out by the study coordinator and the local research nurses, using internal consistency checks and identification of database entries outside expected ranges.

Statistical analysis will be performed using IBM SPSS, R, Python, and Excel. Subject characteristics will be presented and analysed using descriptive statistics. Continuous parameters will be presented as means and standard deviations, and assessed between the two groups (taVNS vs. sham) with a two-sample unpaired t-test (for normally distributed data) or a nonparametric Mann-Whitney U test (for non-normally distributed data). Categorical variables will be represented as frequencies and analyzed using a Chi-square test or a Fisher's exact test. A p-value < 0.05 will be considered statistically significant.

Data interpretation will involve effect size estimates as appropriate for each statistical test (e.g. Cohen's *d* for t-tests, *f* for Mann-Whitney U test) as well as estimated intervals, such as 95% confidence intervals. Thereby, conclusions will not be drawn from a singular p-value alone. No missing data are expected. Primary and secondary outcomes data will be analysed based on an intention-to-treat approach.

10.1 Primary study parameter(s)

The efficacy of taVNS in attenuating the acute stress response induced by the validated Maastricht Acute Stress Task (MAST) among healthy subjects will be determined based on cortisol levels in saliva samples, using an intention-to-treat principle. A repeated measures ANOVA will be utilized to evaluate both intergroup differences and within-group changes in cortisol levels across the different time points. If the assumption of normality is violated, a nonparametric equivalent will be employed. Multivariable regression analysis will be performed to correct for confounding effects of age, gender, and mental health (i.e. GAD-7, PHQ-9, BFI). Differences in cortisol saliva levels, with corresponding 95% confidence intervals (CIs) and two-sided p-values, will be calculated at a type I error level of 0.05.

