4.4 Sample size calculation

There are no directly comparable studies available for an accurate sample size calculation, as previous research investigating the effect of tVNS on stress used different stimuli, making comparison challenging. However, previous research on the Maastricht Acute Stress Task (MAST) indicated that 85% of participants demonstrate a noticeable and quantifiable cortisol response (i.e., cortisol increase $\geq 2.5\text{nmol/l}$ from baseline) to the acute stress task (1). Anticipating that tVNS is expected to counteract the cortisol response to the MAST by 35%, resulting in an estimated 85% cortisol increase from baseline in the sham group vs. a 50% increase from baseline in the tVNS group, a sample size of 54 participants is required to detect this difference ($b=0.8$, $\alpha=0.05$). This estimate is consistent with other somewhat similar studies on tVNS. Based on previous experience with studies involving healthy volunteers, an additional six participants (10%) will be recruited to account for potential dropouts. This approach is deemed appropriate and feasible given the short and non-invasive nature of the intervention.

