8.3.3 Biological samples

Saliva cortisol samples: During the study visit, saliva cortisol samples will be collected using synthetic Salivette devices: before the start of either taVNS or sham stimulation (baseline), 5 minutes before (t-pre-stress) and 6 times afterward (t+05, t+15, t+25, t+35, t+45, t+55) the MAST (thus, a total of 8 samples will be collected; see Figure 3). Samples will be processed as soon as possible and will be promptly stored at -20 °C until further analysis. The analysis of the samples will be conducted at the end of the study period in the laboratory of Maastricht University using immunoassay (ELISA SLV-2930). See

F4.4_MAST_SOP_Speekselsamples_Versie1.1_dd 02-01-2025 for a detailed description of the saliva cortisol sample collection process and subsequent processing.

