10.2 Secondary study parameter(s)

The efficacy of taVNS and sham stimulation in alleviating stress-related effects, such as negative affect and feelings of stress, pain, and unpleasantness, will be determined

based on scores on the I-PANAS-SF and the 0-100 Visual Analog Scales (VASs). Scores will be compared between the two groups using the same statistical approach as that for the primary outcome.

To evaluate the effect of taVNS vs. sham on autonomic parameters, such as heart rate variability and skin conductance, a mixed-effects model will also be used. This model allows for the evaluation of the impact of taVNS on each autonomic parameter while accounting for the repeated measure within subjects.

To assess the effect of taVNS vs. sham on pulse rate variability (PRV), as a measure of vagal tone of the autonomous nervous system, all photoplethysmography data files will be processed using a custom-written MATLAB script (MATLAB R2020a). Systolic peaks will be detected using the peak detection method and considered as the pulse times for calculating pulse intervals and PRV. Root mean square of successive differences (RMSSD) will be calculated first for the 6-minute baseline period and then over fixed 5-minute intervals, following standard practice. For statistical analysis, the RMSSD change from pre-intervention (baseline) will be calculated for each subject under each condition (i.e. taVNS and sham). Marginal linear mixed models (using the R lme4 function) will be used to compare RMSSD change from baseline between conditions, using R Statistical Software version 3.6.3 (2020-02-29). RMSSD (change from baseline) will be the dependent variable, with condition (taVNS versus sham) as the within-subject independent variable. Both the main effects and the two-way interaction will be included in the model. Model fit will be assessed using the Kronecker product of an unstructured and a first-order autoregressive variance-covariance matrix, based on the lowest value of Akaike's Information Criterion. The main effect of condition will test the hypothesis of a significant difference in RMSSD between conditions over the entire time course.

Furthermore, HRV data obtained from the FitBit and Shimmer3 GSR will be compared for accuracy using linear mixed-effects models.

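### As conventionally fitted, the primary repeated measures ANOVA drops any finisher lacking one of eight cortisol values, so the analysed set can be smaller than the intention-to-treat set

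*Protocol*

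**What the plan says.** Section 10.1 fixes the primary method: "A repeated measures ANOVA will be utilized to evaluate both intergroup differences and within-group changes in cortisol levels across the different time points". It places that analysis under intention to treat ("using an intention-to-treat principle") and allows an unnamed nonparametric equivalent if normality fails. Section 8.3.3 sets the number of saliva samples per participant: "thus, a total of 8 samples will be collected; see Figure 3". They are one baseline sample before stimulation, one before the stressor and six after it.

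Section 10 covers missing data and the analysis population in two consecutive sentences: "No missing data are expected. Primary and secondary outcomes data will be analysed based on an intention-to-treat approach". It gives no rule for a sample that is missing or cannot be assayed.

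Three other places bear on the point:

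- Section 4.4 adds a recruitment margin: "an additional six participants (10%) will be recruited to account for potential dropouts".
- Section 8.5 leaves out of the analysis anyone who stops before the procedures are complete, and lets the researchers replace such a person during recruitment. It does not mention a participant who finishes but has a failed sample.
- Section 10.2 applies the primary outcome's approach to I-PANAS-SF and VAS, but uses a mixed-effects model for the autonomic outcomes: "This model allows for the evaluation of the impact of taVNS on each autonomic parameter while accounting for the repeated measure within subjects".

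**The concern.** A conventional repeated measures ANOVA works on one complete vector per participant. If one of eight cortisol values is absent and nothing is imputed, the other seven are discarded with it. A randomised, treated participant who sat through the whole session would then be missing from an analysis labelled intention to treat. The fallback has the same weakness, because the usual nonparametric tests for repeated measures also need complete blocks.

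The loss comes from the estimator and is separate from the rule on early leavers in Section 8.5. Correcting that rule would not cure it.

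Two things are at stake. One is the number analysed, since failed samples draw on a margin of six that was set aside for dropouts. The other is bias: a complete-case analysis is in general unbiased only if loss is completely at random. A model that uses all available samples needs only the weaker missing-at-random assumption.

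**Working it through.** **1. The plan's own figure.** Inputs are the responder rates of 85% (sham) and 50% (taVNS) from the Summary, the 80% power and alpha 0.05 from Section 4.4, the two-sided testing from Section 10.1, and 1:1 allocation. With pooled variance and no continuity correction:

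n per arm = [1.960 × √(2 × 0.675 × 0.325) + 0.842 × √(0.85 × 0.15 + 0.50 × 0.50)]² / 0.35² = (1.298 + 0.517)² / 0.1225 ≈ 26.9, so 27 per arm and 54 in total.

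Power at 27 per arm is 80.2%. Dividing 54 by 0.90 gives 60. Both stated totals reproduce, as a comparison of two proportions.

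**2. Does the method need complete data?** A test with the AnovaRM routine in statsmodels, on 10 subjects by 8 times, ran with complete data. After one value was removed it stopped with an error that the data were unbalanced.

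**3. Share of finishers lost, independent failures.** Let m be the chance that any one sample is unusable. The documents give no value, so m is an assumption. The share with at least one gap is 1 − (1 − m)^8.

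| m | Share lost | Complete, of 60 finishers | Complete, of 54 finishers |
|---|---|---|---|
| 0.5% | 3.9% | 57.6 | 51.9 |
| 1% | 7.7% | 55.4 | 49.8 |
| 2% | 14.9% | 51.0 | 45.9 |

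**4. Share lost if failures cluster.** Too little saliva, for example, is likely to recur in the same person. Take a beta-binomial with within-person correlation 0.3 (also an assumption), with a = m × 0.7/0.3 and b = (1 − m) × 0.7/0.3. The share lost is 1 − Π (b + i)/(a + b + i) for i = 0 to 7. This gives 3.8% at m = 1% and 7.5% at m = 2%, about half the independent figures.

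**5. When is the margin of six used up?** If all 60 finish and failures are independent, 54 complete vectors remain when (1 − m)^8 = 54/60. So m = 1 − 0.9^(1/8) = 1.3%. With clustering, a higher rate is needed.

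**6. Power, for illustration only.** Putting the independent-failure counts into the two-proportion calculation of step 1 gives 81.2% (m = 1%) and 77.8% (m = 2%) from 60 finishers. From 54 finishers it gives 76.7% and 73.1%. These figures do not carry over to the planned test, because the ANOVA is not what was sized.

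**The case against.** The strongest reply is that deletion is inferred. Section 10.1 names the ANOVA but does not say that incomplete series are dropped, that nothing is imputed, or that all eight samples enter. A statistical analysis plan that is not shown could add a rule, and samples are taken in one supervised session of 2–3 hours, so failures may be few. This stands as a limit: the point holds for the ANOVA as conventionally fitted. It does not remove the point, because the protocol itself chose the method, assumed complete data and claimed intention to treat, and these stop fitting together once one sample fails. The reference to the different time points names no subset.

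Three stronger readings are tempting, and the documents do not support them:

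- A reader might infer that a finisher with a gap can never be analysed. That is true only of a fit without imputation.
- A reader might take a 5% failure rate, conclude that about a third of finishers (1 − 0.95^8 = 34%) would be lost, and add a large fall in power. No rate is documented, independence is near the worst case, and starting from 54 assumes six unreplaced dropouts although Section 8.5 allows replacement.
- A reader might see a flat contradiction between expecting no missing data and planning for 10% dropouts. Under Section 8.5 early leavers are left out of the analysis, so the authors may have meant that those analysed would be complete. Leaving them out does conflict with intention to treat, but that is a separate matter.

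**Conclusion.** The point holds in a limited form. The protocol pairs an estimator that, as usually fitted, needs complete series with an unsupported expectation of complete data and an intention-to-treat label. A finisher with one failed sample would be removed, and validity would then generally require loss completely at random.

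The size is unknown. At assumed failure rates of 1% to 2% per sample, between about 4% and 15% of finishers would be lost, depending on how strongly failures cluster. The recruitment margin of six would be used up by sample failures alone only at about 1.3% per sample or more, and that assumes independence and no dropouts. No loss of power can be claimed for the planned test. The change is still worth making, because it costs little and gives similar inference when the data are complete.

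**What to change.** In Section 10.1, replace the repeated measures ANOVA with a linear mixed model for repeated cortisol:

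- **Terms and estimation:** arm, time and arm by time, fitted by REML with Kenward-Roger or similar degrees of freedom.
- **Covariance:** unstructured, with a simpler fallback stated in advance. Eight time points mean 8 × 9/2 = 36 covariance parameters for 54 to 60 people, so the fallback may be needed.
- **Population:** all randomised participants with any available cortisol sample. Section 8.5 must be aligned with this.
- **Non-normal residuals:** log-transformed cortisol in the same model, instead of a nonparametric test that needs complete blocks.
- **Software:** a procedure that supports residual covariance structures. The lme4 routine named in Section 10.2 does not directly fit an unstructured one.

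Use the same model for I-PANAS-SF and VAS. In Section 10, replace the sentence "No missing data are expected" with a statement that all available data are used under a missing-at-random assumption.

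No participants, visits or samples are added. The downside is slightly more analysis work and a covariance choice to pre-specify. Section 10.2 already uses this class of model.

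### The primary cortisol test may change, after the data are seen, to an unnamed nonparametric method on a normality check with no stated scale or trigger

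*Protocol*

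**What the plan says.** Protocol section 10.1 sets the primary analysis: "A repeated measures ANOVA will be utilized to evaluate both intergroup differences and within-group changes in cortisol levels across the different time points". The fallback follows at once: "If the assumption of normality is violated, a nonparametric equivalent will be employed".

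The same section then asks for two further things:
- an adjusted analysis: "Multivariable regression analysis will be performed to correct for confounding effects of age, gender, and mental health (i.e. GAD-7, PHQ-9, BFI");
- an estimate: "Differences in cortisol saliva levels, with corresponding 95% confidence intervals (CIs) and two-sided p-values, will be calculated at a type I error level of 0.05".

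The opening of section 10 names one rank test, in its general text on comparing continuous parameters between the two groups: "a nonparametric Mann-Whitney U test (for non-normally distributed data"). Section 10.2 carries the section 10.1 approach to the I-PANAS-SF and the VAS: "Scores will be compared between the two groups using the same statistical approach as that for the primary outcome".

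The Protocol does not say whether normality is judged on raw values or residuals, pooled or per group and time point, or by what criterion. It mentions no transformation of cortisol and gives no SD, CV or skewness for it.

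**The concern.** The primary test is conditional on the outcome data. Two analysts who follow section 10.1 faithfully could check normality differently, reach different decisions, and then choose different replacement tests. The method behind the headline p-value would not be fixed in advance.

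The condition could well be met. Cortisol is a positive concentration, and such quantities are often right-skewed on the raw scale. If the switch happens, the substitutes most analysts would reach for do not do the job of a two-group repeated measures analysis. The promised cortisol difference with its interval would also no longer come from the same analysis as the p-value.

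**Working it through.** **Inputs from the Protocol.** Eight saliva samples per participant (section 8.3.3), 1:1 allocation (section 8.2), and 54 participants required, with 60 recruited (section 4.4).

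**The plan's own figure.** The 54 follows from comparing 85% with 50% at two-sided 0.05 and 80% power, without continuity correction:

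n per arm = [1.960·√(2·0.675·0.325) + 0.842·√(0.85·0.15 + 0.50·0.50)]² / 0.35² = (1.298 + 0.517)² / 0.1225 ≈ 26.9, rounded up to 27, so 54 in total; 54/0.9 = 60.

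It is used here only to set 27 per arm.

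**Assumptions not in the Protocol.** Cortisol is lognormal with log-SD = √ln(1 + CV²), so CV 0.2 gives √ln 1.04 = 0.198 and CV 0.6 gives √ln 1.36 = 0.555. Within-subject correlation on the log scale is 0.7. The check is Shapiro-Wilk at 0.05.

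**Step 1: how often would the check fail?** Simulated rejection rates (2,000 trials; 500 for the last column):

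| CV | one arm, one time (n = 27) | residuals of both arms, one time (n = 54) | any of the 16 arm-by-time cells |
|---|---|---|---|
| truly normal | 5% | 5% | 52% |
| 0.2 | 18% | 32% | 89% |
| 0.3 | 33% | 58% | 97% |
| 0.4 | 49% | 78% | 99% |
| 0.5 | 64% | 90% | 100% |
| 0.6 | 73% | 96% | 100% |

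Down the middle column, the chance of switching runs from 32% to 96% over the assumed CV range. Across the CV 0.2 row, the same data-generating model gives 18%, 32% or 89% depending only on how the check is done. Even with truly normal data it is 5% or 52%. The undefined check therefore matters as much as the unknown skewness.

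**Step 2: what would the switch lead to?** Simulation with no arm difference, log-SD 0.5, correlation 0.7, 27 per arm, an assumed stress curve over the eight samples, 2,000 runs, nominal level 5%. The simulation standard error near 5% is √(0.05·0.95/2000) ≈ 0.5 percentage points.

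| Test | Rejects | What it compares |
|---|---|---|
| Friedman, pooled sample | 100% | time only; it has no arm term |
| Mann-Whitney on baseline-corrected area under the curve | 4.4% | arms, on one summary |
| Rank-based ANOVA-type statistic (Brunner-Langer) | 4.4% | arm by time |
| Repeated measures ANOVA, raw scale, Greenhouse-Geisser | 3.7% | arm by time |
| Repeated measures ANOVA, log scale, Greenhouse-Geisser | 4.7% | arm by time |

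Friedman's 100% is not a false-positive rate for treatment. It detects the stress curve, which is present in both arms, and says nothing about taVNS against sham. Mann-Whitney is valid for one summary per participant, but the Protocol defines neither a cortisol summary nor a primary time point. In this setting the raw-scale ANOVA did not exceed its nominal level, so the switch was not needed to protect it.

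**Step 3: the other outputs of section 10.1.** Neither Friedman nor Mann-Whitney takes covariates. Friedman yields no arm difference at all. After a switch, the p-value and the adjusted difference would come from different analyses.

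**The case against.** Much of the case against stands, and it limits the point.

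- **A reader might infer that no nonparametric method exists for this design.** That is wrong. Rank-based ANOVA-type statistics test arm by time, can be run in R, which section 10 lists ("Statistical analysis will be performed using IBM SPSS, R, Python, and Excel"), and held their level above. Mann-Whitney on a per-participant area under the curve is also a valid arm comparison.
- **A reader might infer that the switch is almost certain.** The documents do not support this. They give no spread or skewness for cortisol and no check. The figure depends on both.
- **A reader might infer an inflated type I error.** Uncorrected Mann-Whitney tests at all eight samples would give at least one false positive in 19.3% of simulated null trials. The Protocol never states that analysis. Mann-Whitney appears only in the general text of section 10, and Friedman appears nowhere.
- **A reader might take arm by time to be the Protocol's primary contrast.** Section 10.1 refers only to differences between groups and changes within groups. On any reading, however, a between-arm comparison is needed, and Friedman has none.
- **Mann-Whitney can be paired with a Hodges-Lehmann shift and its interval.** The adjusted regression is also a separate sentence in section 10.1. So it is too strong to say that no interval could be had; what is lacking is a covariate-adjusted difference from the test itself.
- **The name of the test, the check and any transformation may stand in a statistical analysis plan that is not shown.** Their absence alone is no finding. What remains is the rule that the Protocol does fix: the primary test depends on the outcome data. Naming the second test elsewhere would not remove that dependence.

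**Conclusion.** The point holds in a limited form. Section 10.1 fixes a data-driven change of the primary test to an unnamed method on an undefined check, and section 10.2 extends it to the I-PANAS-SF and the VAS.

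The switch is plausible rather than certain: about 32% to 96% for Shapiro-Wilk on 54 residuals at one time, assuming lognormal cortisol with a CV of 0.2 to 0.6. Those inputs are assumptions, not Protocol figures. The two common rank substitutes do not serve the primary question as the Protocol now stands, although suitable rank methods exist. No particular inflation of the type I error can be attributed to the plan. The defect is that the primary method is not settled before the data are seen, and it is cheap to repair.

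**What to change.** Replace the fallback sentence in section 10.1 with one prespecified primary analysis:

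- Analyse natural-log cortisol in a linear mixed (or repeated measures) model with arm, time, arm by time and the baseline sample.
- Name one between-arm contrast in advance, for example the mean difference over the six samples after the MAST. Report it as a ratio of geometric means with 95% CI and two-sided p-value.
- State that the test does not change on the result of any normality check.
- If a permutation p-value or bootstrap interval is wanted for the same contrast, make it a prespecified sensitivity analysis that is always reported, not one triggered by the residuals.

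In section 10.2, state the method for the I-PANAS-SF and the VAS separately, without a normality-triggered switch. Logs are not an automatic choice for scales that can take the value zero, as the 0-100 VAS can.

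**Cost.** A few sentences and no new data. Section 10.2 already uses mixed models for the autonomic parameters, so the method is within the team's reach, but section 10.1 has none for cortisol and the model must be written out there. Effects become ratios, so the section 10.1 wording about differences in cortisol levels must be aligned. The 35% threshold in section 8.1.1 should be expressed on the same scale.

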Objective: The primary aim of this study is to assess the efficacy of taVNS in mitigating the acute stress response induced by the Maastricht Acute Stress Task (MAST) among healthy subjects, measured by cortisol levels in saliva samples. It is hypothesized that taVNS will significantly reduce the cortisol response to the MAST by 35%. Since prior research showed that 85% of healthy participants exhibited a measurable cortisol response ((i.e. cortisol increase ≥ 2.5 nmol/l) to the MAST, a responder rate of 85% is expected in the sham group compared to 50% in the taVNS group (1).

Secondary objectives include evaluating taVNS's potential to counteract stress-induced sympathetic activation, thereby reducing negative affect as measured by the International Positive and Negative Affect Schedule Short Form (I-PANAS-SF), as well as feelings of stress, pain, and unpleasantness, on 0-100 Visual Analog Scales (VAS). Additionally, the study will assess taVNS's impact on autonomic outflow parameters and examine the relationship between stress responses and affective symptoms and personality trait, using the Generalized Anxiety Disorder 7-Item Scale (GAD-7), Patient Health Questionnaire (PHQ-9), and the Big Five Inventory (BFI).

Study design: This study concerns a single-centre, prospective, double-blind, randomized, placebo-controlled interventional trial with a (1:1) parallel design, with all measurements conducted at Maastricht University.

Study population: This study aims to enrol 60 healthy volunteers aged 18-65 years.

Intervention: Participants will be randomly assigned to either the taVNS or sham stimulation group, administered 30 minutes before the MAST.

Main study parameters/endpoints: The primary endpoint is a significant reduction in the neuroendocrine stress response, measured by saliva cortisol samples, in the taVNS group compared to the sham treatment group following the MAST.

Nature and extent of the burden and risks associated with participation, benefit and group relatedness:

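### The primary cortisol analysis adjusts for age, gender and psychological scales but not for pre-stimulation cortisol, and if the group main effect is the deciding test, the untreated baseline sample dilutes it

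*Protocol*

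**What the plan says.** Protocol section 10.1 gives the primary model: "A repeated measures ANOVA will be utilized to evaluate both intergroup differences and within-group changes in cortisol levels across the different time points". It then adds a second analysis: "Multivariable regression analysis will be performed to correct for confounding effects of age, gender, and mental health (i.e. GAD-7, PHQ-9, BFI"). Differences with 95% confidence intervals and "two-sided p-values, will be calculated at a type I error level of 0.05" are promised.

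Section 8.3.3 defines the samples: "before the start of either taVNS or sham stimulation (baseline), 5 minutes before (t-pre-stress) and 6 times afterward" (t+05 to t+55), eight in all. The first precedes any stimulation. The second follows stimulation but precedes the stress phase.

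Sections 2.1 and 4.4 state the hypothesis as a rise from baseline: "resulting in an estimated 85% cortisol increase from baseline in the sham group vs. a 50% increase from baseline in the tVNS group".

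No section makes the pre-stimulation cortisol value a covariate or takes it out of the outcome. Section 10.1 does not say which ANOVA term tests the hypothesis. For RMSSD, by contrast, section 10.2 analyses change from baseline and names the term that carries the test. Section 10.2 also applies the primary approach to the I-PANAS-SF and VAS scores.

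**The concern.** Baseline cortisol is the obvious candidate predictor of later cortisol, it is collected from everyone, and it precedes treatment. A covariate list that includes anxiety, depression and personality scales but omits this value may give up precision that costs nothing.

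The pre-stimulation sample also cannot carry a treatment effect. If it is one of the levels over which the group main effect is averaged, it pulls the estimated difference towards zero. That main effect is a difference in average level, whereas the hypothesis is about a rise from baseline. At stake is whether a trial of 54 evaluable participants can detect the effect it was set up to find.

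**Working it through.** **1. The plan's own figure.** Section 4.4 states that "a sample size of 54 participants is required to detect this difference". The 85% comes from a responder rate ("85% of participants demonstrate a noticeable and quantifiable cortisol response"), and the Summary gives the contrast in that form: "a responder rate of 85% is expected in the sham group compared to 50% in the taVNS group". The two-proportion formula with pooled variance, two-sided 0.05 and 80% power gives

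n per arm = [1.960 × √(2 × 0.675 × 0.325) + 0.842 × √(0.85 × 0.15 + 0.50 × 0.50)]² / 0.35² = 26.9, so 27 per arm and 54 in total.

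The figure reproduces, and 54/0.90 = 60 matches enrolment. But it is a calculation for proportions. It uses no cortisol SD and no correlation between samples, so it says nothing about the power of the ANOVA.

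**2. Dilution of the main effect.** For a constant effect d after treatment, the mean over eight samples carries 7d/8 = 0.875d. If t-pre-stress also shows no effect, it carries 6d/8 = 0.75d.

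**3. Power at 27 per arm.** Assumed: unit SD at each sample, no missing data, and correlation r either equal between all samples (CS) or decaying by step (AR). The effect is equal on the six post-stress samples and zero before, and is scaled so that the baseline-adjusted mean of those six has 80% power. For a mean over samples, noncentrality = (mean effect) × √(27/2) / √V.

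Example, CS with r = 0.5 and d = 0.45, where √13.5 = 3.674:
- Main effect, eight samples: V = (1 + 7r)/8 = 0.5625; 0.75 × 0.45 × 3.674/0.750 = 1.65; power 37%.
- Mean of the six post-stress samples, unadjusted: V = (1 + 5r)/6 = 0.583; 0.45 × 3.674/0.764 = 2.16; power 57%.
- The same mean adjusted for baseline: V = 0.583 − 0.5² = 0.333; 0.45 × 3.674/0.577 = 2.86; power 80%.

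Dropping the two unaffected samples therefore gains 20 points, and adjusting for baseline gains a further 23.

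| Correlation | Main effect, 8 samples | Post-stress mean, unadjusted | Adjusted, 7 later samples | Adjusted, 6 post-stress | Group-by-time (Greenhouse-Geisser) | Group-by-time (multivariate) |
|---|---|---|---|---|---|---|
| CS 0.3 | 50% | 71% | 69% | 80% | 36% | 32% |
| CS 0.5 | 37% | 57% | 69% | 80% | 51% | 45% |
| CS 0.7 | 24% | 38% | 68% | 80% | 65% | 58% |
| CS 0.9 | 11% | 16% | 68% | 80% | 75% | 69% |
| AR 0.3 | 67% | 81% | 74% | 80% | 22% | 17% |
| AR 0.7 | 59% | 76% | 75% | 80% | 45% | 43% |
| AR 0.9 | 35% | 53% | 75% | 80% | 66% | 83% |

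**4. Other effect shapes.** If the effect rises and falls over the post-stress samples (0.6, 1, 1, 0.8, 0.5, 0.3 of peak), group-by-time power is 34% to 93% (Greenhouse-Geisser) or 23% to 94% (multivariate). At CS 0.8 it is 90% and 85%, against 80% for the adjusted mean. If the full effect is already present at t-pre-stress, the main effect has 14% to 80%, the adjusted seven-sample mean 81% to 87%, and group-by-time 14% to 48% (Greenhouse-Geisser) or 13% to 83% (multivariate).

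**5. Simulation with a fixed effect.** Assumed: peak effect 0.7 SD, random intercept plus AR(1), zero effect at both samples before stress, and 0.6 to 1.0 of peak afterwards. The average baseline-to-post correlation was 0.26 / 0.44 / 0.63. Ranges are over repeat runs.
- Group main effect: 54–55% / 47–49% / 43%.
- Group-by-time: 56–60% / 69–74% / 87–90%.
- Baseline-adjusted post-stress mean: 74–76% / 77–80% / 85–87%.

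With no true effect, calling the trial positive when either the main effect or the interaction is significant gave 8.2% to 9.1% type I error.

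**The case against.** The strongest defence is that the hypothesis concerns change from baseline, so the matching ANOVA term is group-by-time. There the pre-stimulation sample is the reference for change and dilutes nothing. That stands. It also stands that inclusion of this sample among the ANOVA levels is inferred from the wording rather than stated, and that naming the deciding term is often left to a SAP.

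A reader might infer four stronger things that the protocol does not support:
- **That power is lost whichever term decides.** At high correlation the interaction equals or beats the adjusted mean (87–90% against 85–87% in step 5).
- **That the plan throws the baseline sample away.** A repeated measures ANOVA with baseline as a level uses it through within-person differences, though often less efficiently than covariate adjustment.
- **That the type I error is nearly 10%.** The value 1 − 0.95² = 9.75% needs two independent tests and a rule that either one suffices. Section 10.1 states no such rule, and section 10 says conclusions will not rest on one p-value. The simulated figure under that hypothetical rule is 8% to 9%.
- **That adjusting for the psychological scales is invalid.** Calling them confounders is loose in a randomised trial, but prognostic adjustment is legitimate.

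The dilution figure also depends on what happens at t-pre-stress. With an assumed effect there of 0.6 of peak, main-effect power rises to 64% / 57% / 51%, while the interaction falls to 36% / 50% / 67%.

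None of this answers the narrower point. The protocol does fix a covariate list, and that list leaves out the pre-treatment value of the outcome.

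**Conclusion.** The point holds in a limited form. The omission of baseline cortisol from the stated covariates is certain. Its treatment as an outcome level is the natural reading.

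If the main effect decides, power was below that of a baseline-adjusted analysis of the seven later samples in every scenario tried. With an equal post-stress effect the gap was 7 points (67% against 74%) to 57 points (11% against 68%). Against the adjusted six-sample mean the gap was 13 to 69 points. It closed only with weak AR correlation (0.3) and the full effect already present at t-pre-stress, where both had 80%.

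If group-by-time decides, there is no dilution. The test is weaker than the adjusted mean at low to moderate correlation and similar or better at high correlation. As an omnibus test over eight times it does not supply the single difference with a confidence interval that a primary result needs.

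The gain from the covariate itself also depends on correlation: none at AR 0.3 (81% unadjusted, 80% adjusted), 23 points at CS 0.5. The protocol gives no cortisol SD, correlation or effect profile, so these are ranges under assumptions and not estimates for this trial.

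**What to change.** In section 10.1, name one primary contrast: the arm difference averaged over the six post-stress samples (t+05 to t+55), with its 95% confidence interval. Take it from a mixed model with arm, time and arm-by-time, adjusted for pre-stimulation cortisol, age and sex. Do not adjust for t-pre-stress, because it follows stimulation and may itself be affected. Report the arm-by-time test as supportive. Keep the GAD-7, PHQ-9 and BFI adjustment as a sensitivity analysis, or handle it under secondary objective 3. Use the pre-stimulation score in the same way for I-PANAS-SF and VAS, since section 10.2 takes over the primary approach.

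The cost is a change of wording: no new samples, visits or participants. The one statistical price is some power against the interaction test if the effect varies sharply over time and correlation is high, for example 80% against 90% at CS 0.8 in step 4.
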